#### **By MedDRA Term:**

- Number (%) of subjects reporting TEAEs by organ class and preferred term
- Number (%) of subjects reporting Grade 3 or 4 TEAEs by organ class and preferred term
- Number (%) of subjects reporting treatment-related AEs by organ class and preferred term
- Number (%) of subjects reporting treatment-emergent SAEs by organ class and preferred term
- Number (%) of subjects reporting treatment-emergent non-serious AEs by organ class and preferred term

In addition, a listing of DLTs will be provided.

These TEAEs occurring in 2 or more subjects in the safety population will be summarized by the Medical Dictionary for Regulatory Activities (MedDRA) preferred term for all causalities as well as for treatment-related causalities.

Proportion of subjects with new onset of Grade 4 thrombocytopenia events based on laboratory data and as measured by CTCAE grades will be summarized. The hazard function of time to onset of Grade 4 thrombocytopenia will be estimated using life table method.

Proportion of subjects with new onset of Grade 2 or higher hemorrhage based on preferred terms included in the Standardized MedDRA Query (SMQ) for “Haemorrhage terms (excluding laboratory terms) (SMQ)” and as measured by CTCAE grades will be summarized. The hazard functions of time to onset will be estimated using life table method.

Proportion of subjects with new onset of Grade 4 anemia based on laboratory data and as measured by CTCAE grades will be summarized. The hazard functions of time to onset will be estimated using life table method.

For the above 3 types of AEs, additional analyses using summary tables as well as data listings may be provided taking into account the blood transfusion status at baseline and post-baseline blood transfusion history.

Selected maximal severity AE summary tables will also be generated by the dose level the subject received.

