**NOTE TO THE PROGRAMMER: Table is continued to Week 48 as long as data is available.**

PROTOCOL: INCB 18424-258  
DRUG/INDICATION: Ruxolitinib/Myelofibrosis

(Page 1 of 1)  
VERSION: Final

Table 14.3.2.1

Overall Summary of Treatment-Emergent Adverse Events by Dose Ever Received  
(Population: Safety Evaluable Subjects)

Variable	All Subjects (N=23)	Dose Level (mg) Subjects Ever Received				
		<=5 (N=2)	>5 10 (N=23)	>10 15 (N=14)	>15 20 (N=7)	>20 25 (N=1)
Treatment-Emergent Adverse Events (TEAE) Reported	33	1	8	21	3	0 ( 0.0)
Subjects with a TEAE	10 ( 43.5)	1 ( 50.0)	3 ( 13.0)	5 ( 35.7)	1 ( 14.3)	0 ( 0.0)
Subjects with a Treatment-Related TEAE	2 ( 8.7)	0 ( 0.0)	1 ( 4.3)	1 ( 7.1)	0 ( 0.0)	0 ( 0.0)
Subjects with a Serious TEAE	2 ( 8.7)	1 ( 50.0)	0 ( 0.0)	1 ( 7.1)	0 ( 0.0)	0 ( 0.0)
Subjects with TEAE of Grade 3 or Higher	4 ( 17.4)	1 ( 50.0)	1 ( 4.3)	2 ( 14.3)	0 ( 0.0)	0 ( 0.0)
Subjects with a Dose Increase Due to TEAE	0 ( 0.0)	0 ( 0.0)	0 ( 0.0)	0 ( 0.0)	0 ( 0.0)	0 ( 0.0)
Subjects with a Dose Reduction Due to TEAE	1 ( 4.3)	0 ( 0.0)	0 ( 0.0)	1 ( 7.1)	0 ( 0.0)	0 ( 0.0)
Subjects with Procedures Performed Due to TEAE	2 ( 8.7)	0 ( 0.0)	0 ( 0.0)	2 ( 14.3)	0 ( 0.0)	0 ( 0.0)
Subjects with a TEAE requiring Concomitant Medication	5 ( 21.7)	0 ( 0.0)	1 ( 4.3)	4 ( 28.6)	0 ( 0.0)	0 ( 0.0)
Subjects with Study Drug Withdrawn Due to TEAE	0 ( 0.0)	0 ( 0.0)	0 ( 0.0)	0 ( 0.0)	0 ( 0.0)	0 ( 0.0)
Subjects with an TEAE Leading to Discontinuation from the Study	0 ( 0.0)	0 ( 0.0)	0 ( 0.0)	0 ( 0.0)	0 ( 0.0)	0 ( 0.0)
Subjects with a TEAE Leading to Death	0 ( 0.0)	0 ( 0.0)	0 ( 0.0)	0 ( 0.0)	0 ( 0.0)	0 ( 0.0)

PROGRAM\OUTPUT: T\_AESUM1.SAS\T\_AE1.LST

DATE(TIME): 12DEC11(11:30)

Note 1:TEAEs: AEs that began or worsened from baseline following the first administration of the study drug.

Note 2:Treatment-Related AEs:TEAEs with a possible, probable, definite, or missing causality.

Note 3:Severity vs CTCAE Grade: Mild=Grade 1, Moderate=Grade 2, Severe=Grade 3, Life-Threatening=Grade 4.

Note 4:For an AE that occurred for more than once to a subject, it is counted in the lowest dose when the highest severity grade is recorded.

Reference: Listings 16.2.7.2.1

NOTE to the reviewer: numbers in the shell is from draft DMC output and is intended to show shell only.

PROTOCOL: INCB 18424-258  
DRUG/INDICATION: Ruxolitinib/Myelofibrosis

(Page 1 of 1)  
VERSION: First DMC-Draft

Table 14.3.2.2.1

Summary of Subjects Reporting Treatment-Emergent Adverse Events (All Causalities) by  

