MedDRA System Organ Class, Preferred Term, and Maximum Severity  
(Population: Safety Evaluable Subjects)

NOTE TO THE PROGRAMMER: shell will following the standard output.

- Reference: 16.2.7.2.1

PROTOCOL: INCB 18424-258  
 DRUG/INDICATION: Ruxolitinib/Myelofibrosis

(Page 1 of 1)  
 VERSION: First DMC-Draft

Table 14.3.2.2.2

Summary of Subjects Reporting Treatment-Emergent Adverse Events (All Causalities) by  
 MedDRA System Organ Class, Preferred Term, and Dose Level Ever Received  
 (Population: Safety Evaluable Subjects)

Variable	All Subjects (N=23)	CTCAE Grade				
		0 (N=2)	>5 10 (N=23)	>10 15 (N=14)	>15 20 (N=7)	>20 25 (N=1)
Number (%) of Subjects With Any TEAEs	10 ( 43.5)	1 ( 50.0)	3 ( 13.0)	5 ( 35.7)	1 ( 14.3)	0 ( 0.0)
Blood and lymphatic system disorders	1 ( 4.3)	0 ( 0.0)	0 ( 0.0)	1 ( 7.1)	0 ( 0.0)	0 ( 0.0)
Anaemia	1 ( 4.3)	0 ( 0.0)	0 ( 0.0)	1 ( 7.1)	0 ( 0.0)	0 ( 0.0)
Gastrointestinal disorders	6 ( 26.1)	0 ( 0.0)	0 ( 0.0)	4 ( 28.6)	2 ( 28.6)	0 ( 0.0)
Abdominal pain	2 ( 8.7)	0 ( 0.0)	1 ( 4.3)	1 ( 7.1)	0 ( 0.0)	0 ( 0.0)
Anorectal discomfort	1 ( 4.3)	0 ( 0.0)	0 ( 0.0)	1 ( 7.1)	0 ( 0.0)	0 ( 0.0)
Diarrhoea	3 ( 13.0)	0 ( 0.0)	0 ( 0.0)	2 ( 14.3)	1 ( 14.3)	0 ( 0.0)
Dry mouth	1 ( 4.3)	0 ( 0.0)	0 ( 0.0)	0 ( 0.0)	1 ( 14.3)	0 ( 0.0)
Haemorrhoidal haemorrhage	1 ( 4.3)	0 ( 0.0)	0 ( 0.0)	1 ( 7.1)	0 ( 0.0)	0 ( 0.0)
Nausea	1 ( 4.3)	0 ( 0.0)	0 ( 0.0)	1 ( 7.1)	0 ( 0.0)	0 ( 0.0)
. . . . .						
PROGRAM\OUTPUT: T_AESUM1.SAS\T_AE2.LST		DATE (TIME): 12DEC11(11:30)				

Note 1:TEAEs: AEs that began or worsened from baseline following the first administration of the study drug.  
 Note 2:N=the number of subjects who ever took a dose within the dose group, based on which the percent is calculated.  
 Note 3:For an AE that occurred for more than once to a subject, it is counted in the lowest dose when  
 the highest severity grade is recorded.  
 Reference: Listings 16.2.7.2.1

NOTE to the reviewer: numbers in the shell is from draft DMC output and is intended to show shell only.

PROTOCOL: INCB 18424-258  
DRUG/INDICATION: Ruxolitinib/Myelofibrosis

(Page 1 of 1)  
VERSION: First DMC-Draft

Table 14.3.2.3.1

Summary of Subjects Reporting Treatment-Emergent Adverse Events (All Causalities) by  
MedDRA Preferred Term (Sorted by Decreasing Frequency) and Maximal Severity  
(Population: Safety Evaluable Subjects)

NOTE TO THE PROGRAMMER: shell will following the standard output.

- Reference: 16.2.7.2.1

PROTOCOL: INCB 18424-258  

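### AE tables by dose ever received place a subject in one dose column per row but divide by everyone exposed at that dose, so per-dose percentages for recurrent events are too low and the dose pattern is distorted

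*SAP*

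**What the plan says.** The counting rule is in the SAP's table shells (Appendix B). Note 4 of Table 14.3.2.1 and Note 3 of Table 14.3.2.2.2 read: "an AE that occurred for more than once to a subject, it is counted in the lowest dose when the highest severity grade is recorded". Note 2 of Table 14.3.2.2.2 defines the denominator: "N=the number of subjects who ever took a dose within the dose group, based on which the percent is calculated". Table 14.3.2.1 shows the same column sizes. (The header of the 14.3.2.2.2 shell reads as CTCAE grade, but its columns and sizes are the dose groups.) The remaining AE-by-dose tables, 14.3.2.3.2 to 14.3.2.8, have no full shell and are to be programmed in the same way.

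SAP 8.1 announces these tables in one line: "Selected maximal severity AE summary tables will also be generated by the dose level the subject received". SAP 5.2 describes a different grouping. There, AE summaries by dose classify subjects by final titrated total daily dose, with details left to the shells.

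Table 14.3.3.6.1 (Grade 4 thrombocytopenia) uses a related rule: each subject appears once, in the lowest dose group, again over everyone who took a dose in the group. Table 14.3.3.6.2 (Grade 4 anemia) copies it.

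**The concern.** In any one row the numerators are mutually exclusive, while the denominators overlap. All subjects start at 5 mg bid and titrate from there, so many belong to several columns. Take a subject with Grade 1 diarrhea at 10 mg/day and Grade 2 diarrhea at 15 mg/day. That subject is counted at 15 mg/day only, yet stays in the 10 mg/day denominator as if event-free. If both events are the same grade, the tie goes to the lower dose and the higher-dose event drops out of the percentage.

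The rule is also applied separately to the any-TEAE, organ-class and preferred-term rows. One subject can therefore sit in different columns in different rows, and the rows stop agreeing with each other.

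Readers will take these columns as the risk at each dose. Safety and tolerability is a primary objective and an appropriate dosing strategy is a secondary one, so the pattern across dose columns will be interpreted.

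**Working it through.** **1. The shell's own figures.** The numbers are labelled as draft DMC output, shown for layout only. They are used here to see what the rule produces, not to estimate risk.

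| Row | All (23) | ≤5 (2) | >5-10 (23) | >10-15 (14) | >15-20 (7) | >20-25 (1) |
|---|---|---|---|---|---|---|
| Any TEAE | 10 | 1 (50.0) | 3 (13.0) | 5 (35.7) | 1 (14.3) | 0 |
| GI disorders | 6 | 0 | 0 | 4 (28.6) | 2 (28.6) | 0 |
| Abdominal pain | 2 | 0 | 1 (4.3) | 1 (7.1) | 0 | 0 |

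The percentages reproduce, for example 5/14 = 35.7% and 2/7 = 28.6%. The column sizes sum to 2+23+14+7+1 = 47 for 23 subjects. The numerators sum to the All Subjects count: 1+3+5+1+0 = 10, 0+0+4+2+0 = 6 and 0+1+1+0+0 = 2. So numerators are exclusive and denominators overlap.

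**2. Cells that contradict each other.**
- At >15-20, two subjects had a GI event but only one is shown with any event. The any-TEAE cell must be at least 2/7 = 28.6%; it prints 14.3%.
- At >5-10, one subject had abdominal pain but its organ class shows none. The GI cell must be at least 1/23 = 4.3%; it prints 0.0%.

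**3. Size when there is no dose effect.** Assumptions, none from the documents: three doses, 8 weeks each, the same event rate at each, independent Poisson events, and a Grade 1/2/3 mix of 60/25/15%. Let c be the overall proportion with the event and m = −ln(1−c)/3 the mean number of events per dose.

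- True rate at each dose: 1 − e^(−m).
- Printed rate at the j-th dose: the sum over grades g of e^(−3mH) × e^(−(j−1)mq) × (1 − e^(−mq)), where q is the share of grade g and H the share of higher grades. The factors mean: no worse grade anywhere, no equal grade at a lower dose, at least one event of this grade here.

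For c = 28% (the diarrhea rate in Protocol 4.1.5), m = 0.1095 and the true rate is 10.4%. Contributions of Grades 3, 2 and 1:
- dose 1: 0.0163 + 0.0257 + 0.0558 = 9.8%
- dose 2: 0.0160 + 0.0250 + 0.0522 = 9.3%
- dose 3: 0.0158 + 0.0243 + 0.0489 = 8.9%

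The same formula gives:

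| Overall c | True, each dose | Printed, doses 1 / 2 / 3 |
|---|---|---|
| 10% | 3.5% | 3.4 / 3.3 / 3.3% |
| 28% | 10.4% | 9.8 / 9.3 / 8.9% |
| 43.5% (draft any TEAE) | 17.3% | 15.7 / 14.5 / 13.4% |
| 75% | 37.0% | 29.5 / 24.7 / 20.9% |
| 95% | 63.2% | 41.6 / 30.4 / 23.0% |

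**4. Sensitivity of the direction (c = 95%).**
- If grades worsen with dose (80/15/5, then 60/25/15, then 30/40/30%), the printed rates are 28, 30 and 36%: a rise, with the lowest dose losing most.
- With one grade only, the lowest-dose column prints its true 63.2% and the others lose events.

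**5. Unequal time at dose.** With 6, 4 and 14 weeks and c = 95%, the true proportions with an event at each dose are 1 − 0.05^(6/24) = 53%, 1 − 0.05^(4/24) = 39% and 1 − 0.05^(14/24) = 83%. The rule prints 32, 18 and 45%. Correct counting would restore 53, 39 and 83%, which still varies although the weekly risk is constant.

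**The case against.** Counting a subject once at worst grade is ordinary practice for an overall column, and these tables are descriptive. The enrollment holds in Protocol 11.7 use overall percentages. Grade 4 thrombocytopenia and Grade 2 or higher hemorrhage have life-table analyses under SAP 8.1, and platelets have a PK-PD analysis under SAP 9.5. For preferred terms of ordinary frequency the error is about a percentage point. If SAP 5.2 were followed, each subject would sit in one column for both numerator and denominator, and the mismatch would disappear.

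All of this stands as a limit on the consequence. It does not make the percentages right: the shells give the detailed instructions, and nothing reconciles them with SAP 5.2.

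Three stronger readings are tempting but not supported:
- *Higher doses will always look safer.* That needs a similar grade mix across doses; step 4 shows a rise when grades worsen with dose. The draft any-TEAE row (50.0, 13.0, 35.7, 14.3, 0.0%) shows no steady fall either.
- *Every column is understated, and by a lot.* With a single grade the lowest column loses nothing. The 95% overall rate behind the largest figures is an assumption; the only any-TEAE figure in the documents is the early draft 10/23 = 43.5%.
- *Adverse events disappear from the report.* The event-count row still spreads all 33 events across doses ("Treatment-Emergent Adverse Events (TEAE) Reported 33 1 8 21 3", with none in the last column), and Listing 16.2.7.2.1 keeps every event. What is lost is the subject count and its percentage at a dose.

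**Conclusion.** The concern holds as a tabulation error written into the SAP shells. Exclusive numerators over overlapping denominators make per-dose percentages for recurrent events too low, distort the dose pattern, and let rows contradict each other. The mechanism follows from the notes alone; the draft output only illustrates it.

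At 28% overall the shortfall is 0.6 to 1.5 percentage points. Only very common rows, chiefly any TEAE, suffer a large one, roughly a third to two thirds of the true value at an assumed 95% overall. These sizes rest on the assumed grade mix, equal risk, equal time and independence. With equal risk and the same grade mix at each dose, higher doses look falsely safer. If grades worsen with dose, the lower-dose columns lose more events. The correction is cheap and should be made, but it does not affect the co-primary analyses or the safety stopping rules.

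**What to change.** 1. Decide between SAP 5.2 (final titrated dose) and the shells (dose ever received), and make the two agree.
2. If dose ever received is kept, replace the note with: *A subject is counted once per row in each dose column to which at least one such event (onset or worsening) is attributed by the last non-zero dose before the event day (SAP 5.9.3.4), at the worst grade at that dose; dose columns need not sum to All Subjects.* Keep once-per-subject worst-grade counting for the All Subjects column and the maximum-severity tables. Apply this to Tables 14.3.2.1, 14.3.2.2.2, 14.3.2.3.2 to 14.3.2.3.4, 14.3.2.4.2, 14.3.2.5.1 and 14.3.2.6. Tables 14.3.2.7 and 14.3.2.8 (study discontinuation, death) will hardly change.
3. Make the same correction in Tables 14.3.3.6.1 and 14.3.3.6.2. Grade 4 thrombocytopenia is a named safety endpoint.
4. Print patient-time at each dose, or exposure-adjusted rates, beside the columns, because the recount does not correct for unequal time at dose (step 5).

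Cost: a footnote, a small programming change and an exposure line. Dose columns will no longer add up to the total, which the new note states.

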5.2. Secondary Objectives

- To determine an appropriate dosing strategy for patients with low platelets.
- To determine the long-term safety and efficacy effects of ruxolitinib in patients with PMF, PPV-MF, and PET MF who have a baseline platelet count of $50 \times 10^9/L$ to $100 \times 10^9/L$.

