7. INVESTIGATIONAL PLAN

7.1. Overall Study Design

This is an open label study of ruxolitinib in patients with PMF, PPV-MF, and PET-MF. The study is comprised of 4 phases:

| | |
|----------------------------------|--|
| Screening: | Up to 21 days |
| Baseline: | Exactly 7 days |
| Core Treatment Phase: | 24 weeks |
| Extended Treatment Phase: | 132 weeks; subjects receiving benefit will continue ruxolitinib treatment until Week 156 |
| Follow-up Phase: | All subjects will be followed for safety (eg, reporting of AEs and SAEs) for 30 to 37 days after the last dose of study drug is administered |

Core Treatment Phase:

During the core treatment phase, there will be study visits and laboratory-only visits. Subjects will have a regularly scheduled study visit at screening, baseline, Day 1, Week 4, Week 8, Week 12, Week 16, Week 20 and Week 24, where blood samples, assessments, spleen measurements, etc. will be obtained. All hematology labs and coagulation parameters will be analyzed by local laboratories. Serum chemistries, serology, and lipid panel will be analyzed by a central laboratory.

Subjects will have laboratory-only visits to collect hematology lab samples at Week 1, Week 2, Week 3, Week 5, Week 6, Week 7, Week 10, Week 14, and Week 18. The laboratory visits at Week 14 and Week 18 may be skipped for subjects who do not increase their dose at Week 12 or Week 16, and who have maintained platelet counts $> 75 \times 10^9/L$ since the last hematology assessment. Additional, at least weekly laboratory-only visits to collect hematology lab samples will be required if platelet count falls below $35 \times 10^9/L$; more frequent monitoring is recommended if counts fall below $25 \times 10^9/L$. These laboratory visits can occur at the study site laboratory, or any local laboratory that can provide the data and appropriate certificates and normal laboratory ranges to the study site for review for subject management in a timely fashion.

Subjects will have an MRI of the upper and lower abdomen and pelvis to determine the spleen volume at baseline and Week 24. A CT scan will be substituted for subjects who are not candidates for MRI, or when MRI is not readily available. Patients Global Impression of Change (PGIC) questionnaire will be completed monthly. Measurement of spleen length below the left costal margin will be measured by palpation at each study visit.

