8.6.1. Dose Increases

Dose increases are optional.

During the core treatment phase, doses of ruxolitinib may be increased in 5 mg qd increments up to a dose of 10 mg bid starting at the Week 4 visit and at subsequent study visits. Dose increases can occur no more frequently than every 4 weeks, and only if:

- Platelet count was always $\geq 40 \times 10^9/L$ since the last scheduled study visit
- Platelet count, if decreased since the last scheduled study visit, is decreased by no more than 20% of the platelet count at the last scheduled visit
- No dose decreases or holds for safety have occurred during the preceding 4-week interval
- $ANC > 1.0 \times 10^9/L$ since the last scheduled study visit.
- For subjects with prior \geq Grade 2 hemorrhage events, please see below under [Section 8.6.3.4](#), Restarting with Resolution of Hemorrhage Events

Doses may not exceed 10 mg bid except in subjects who continue to meet the above dose escalation criteria, and who have, in addition, a PGIC score of 3 (minimally improved) to 7 (very much worse) while receiving 10 mg bid. Such subjects may continue dose escalation to a maximum dose of 15 mg bid. Note that when a 5 mg qd increment is added, creating a regimen such as 5 mg/10 mg, the higher dose should be taken in the evening and the lower dose in the morning.

During the extended treatment phase, doses of ruxolitinib may be increased in 5 mg qd increments up to a dose of 25 mg bid if the subject meets the above dose escalation criteria, or per the investigator's discretion.

Doses may never exceed 25 mg bid.

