### **5.9.3.4. Last Dose Level Prior to an Adverse Event**

The last dose level prior to an AE is derived as the last non-zero dose (from EX domain) prior to the day an AE occurred. The reason to use “prior to the day” which excludes the day on which an AE occurred is that daily dose is divided into morning and evening doses and no dose administration time is collected on eCRF, making the last dose prior to an AE difficult to verify if “on the same day” dose levels are also included in the derivation.

It is noted that the data collected through the EX domain is treated as actual doses (rather than the prescribed dose schedule, as is the case of deriving compliance, defined earlier). This approach is used throughout when dose-response analyses (for both safety and efficacy) are carried out.

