14.3.1.1	Summary of Exposure and Duration of Exposure to Study Medication Through Week 24	Safety
14.3.1.2	Summary of Exposure to Ruxolitinib Through Week 4	Safety
14.3.1.3	Summary of Average Daily Dose of Ruxolitinib by Study Week	Safety
Safety: Adverse Events		
14.3.2.1	Overall Summary of Treatment-Emergent Adverse Events by Dose Level Ever Received	Safety
14.3.2.2.1	Summary of Subjects Reporting Treatment-Emergent Adverse Events (All Causalities) by MedDRA System Organ Class, Preferred Term, and Maximum Severity	Safety

Table Number	Title	Population
14.3.2.2.2	Summary of Subjects Reporting Treatment-Emergent Adverse Events (All Causalities) by MedDRA System Organ Class, Preferred Term, and Dose Level Ever Received	Safety
14.3.2.3.1	Summary of Subjects Reporting Treatment-Emergent Adverse Events (All Causalities) by MedDRA Preferred Term (Sorted by Decreasing Frequency) and Maximal Severity	Safety
14.3.2.3.2	Summary of Subjects Reporting Treatment-Emergent Adverse Events (All Causalities) by MedDRA Preferred Term (Sorted by Decreasing Frequency) and Dose Level Ever Received	Safety
14.3.2.3.3	Summary of Subjects Reporting Treatment-Emergent Hemorrhage Adverse Events (All Causalities) by MedDRA Preferred Term and Dose Level Ever Received	Safety
14.3.2.3.4	Summary of Subjects Reporting Treatment-Emergent Hemorrhage Adverse Events (All Causalities) of Grade 3 or Higher by MedDRA Preferred Term and Dose Level Ever Received	Safety
14.3.2.4.1	Summary of Subjects Reporting Treatment-Emergent Treatment-Related Adverse Events (All Causalities) by MedDRA System Organ Class, Preferred Term, and Maximum Severity	Safety
14.3.2.4.2	Summary of Subjects Reporting Treatment-Emergent Treatment-Related Adverse Events (All Causalities) by MedDRA System Organ Class, Preferred Term, and Dose Level Ever Received	Safety
14.3.2.5.1	Summary of Subjects Reporting Treatment-Emergent Serious Adverse Events (All Causalities) by MedDRA System Organ Class, Preferred Term, and Dose Level Ever Received	Safety
14.3.2.6	Summary of Subjects Reporting Treatment-Emergent Adverse Events (All Causalities) Leading to Study Medication Decrease or Interruption by MedDRA System Organ Class, Preferred Term, and Dose Level Ever Received	Safety
14.3.2.7	Summary of Subjects Reporting Treatment-Emergent Adverse Events (All Causalities) Leading to Study Discontinuation by MedDRA System Organ Class, Preferred Term, and Dose Level Ever Received	Safety

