14.3.3.1.2	Shift Summary of Laboratory Values in Normal Ranges - Hematology	Safety
14.3.3.2.1	Summary of Laboratory Values – Serum Chemistry	Safety
14.3.3.2.2	Shift Summary of Laboratory Values in Normal Ranges – Serum Chemistry	Safety
14.3.3.3.1	Summary of Laboratory Values – Coagulation	Safety
14.3.3.3.2	Shift Summary of Laboratory Values in Normal Ranges – Coagulation	Safety
14.3.3.4.1	Summary of Laboratory Values – Urinalysis	Safety
14.3.3.4.2	Shift Summary of Laboratory Values in Normal Ranges – Urinalysis	Safety
14.3.3.5.1	Shift Summary of Laboratory Values in CTC Grade - To the Worst Abnormal Value (Tests with One Directional CTC Grade)	Safety
14.3.3.5.2	Shift Summary of Laboratory Values in CTC Grade - To the Worst Abnormal Value (Tests with Two Directional CTC Grade)	Safety

PROTOCOL: INCB 18424-258  
 DRUG/INDICATION: Ruxolitinib/Myelofibrosis

(Page 1 of 1)  
 VERSION: Final

Table 14.3.3.6.1

Summary of Subjects with Treatment Emergent Thrombocytopenia of Grade 4 as Derived from Laboratory Data  
 by Last Dose Before Onset  
 (Population: Safety Evaluable Subjects)

MedDRA Preferred Term	All Subjects (N=xx)	Dose Level (mg) Subjects Ever Received					
		<=5	>5 10	>10 15	>15 20	>20 25	>25
		N=xx	N=xx	N=xx	N=xx	N=xx	N=xx
Number (%) of Subjects With Grade 4 Thrombocytopenia [1]	xx ( xx.x)	xx xx%	xx xx%	xx xx%	xx xx%	xx xx%	xx xx%

PROGRAM\OUTPUT: T\_xxxx.SAS\T\_xxxxx.LST

DATE (TIME) : DDMMYY (HH:MM)

Treatment-Emergent AEs: AEs that began or worsened from baseline following the first administration of study drug.

Note: Subjects are counted only once under in the lowest dose group.

Note: N=the number of subjects who ever took a dose within the dose group, based on which the percent is calculated.

Note: AEs that occurred following the date of treatment crossover were not included.

[1] Grade 4 Thrombocytopenia is defined as any occurrence of a treatment emergent hematology lab below 25 GI/L

Reference: Listing 16.2.8.1.4

PROTOCOL: INCB 18424-258  
DRUG/INDICATION: Ruxolitinib/Myelofibrosis

(Page 1 of 1)  
VERSION: Final

Table 14.3.3.6.2

Summary of Subjects with Treatment Emergent Anemia of Grade 4 as Derived from Laboratory Data  
by Last Dose Before Onset  
(Population: Safety Evaluable Subjects)

NOTE TO THE PROGRAMMER: similarly program this as Table 14.3.3.6.1, just need to update footnote about G4 anemia.

NOTE: the following vital sign tables will be programmed according to standard output.

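### By-dose adverse event tables give crude percentages of subjects ever at each dose; with unequal time at each dose these can create or mask a dose-toxicity pattern, and person-time at dose should be added

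*SAP*

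**What the plan says.** **Denominator.** Note 2 of the Table 14.3.2.2.2 shell (SAP Appendix B) defines N for each dose column as "the number of subjects who ever took a dose within the dose group, based on which the percent is calculated". That shell carries a DMC-draft label, but the Table 14.3.3.6.1 shell (Grade 4 thrombocytopenia), marked final, repeats the note, and Table 14.3.3.6.2 (Grade 4 anemia) is to be programmed like it. SAP Section 10.1 uses the same basis in its titles, for example "Overall Summary of Treatment-Emergent Adverse Events by Dose Level Ever Received".

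**Tables affected.** 14.3.2.1, 14.3.2.2.2, 14.3.2.3.2 to 14.3.2.3.4, 14.3.2.4.2, 14.3.2.5.1 to 14.3.2.8, 14.3.3.6.1 and 14.3.3.6.2. Tables 14.3.2.2.1, 14.3.2.3.1 and 14.3.2.4.1 are by severity and are not part of this point.

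**Numerator.** The adverse event shells state: "For an AE that occurred for more than once to a subject, it is counted in the lowest dose when" the highest grade is recorded. Table 14.3.3.6.1 states: "Note: Subjects are counted only once under in the lowest dose group". SAP Section 5.9.3.4 defines the dose attached to an event as "derived as the last non-zero dose (from EX domain) prior to the day an AE occurred".

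**Titration.** Protocol Section 8.1 starts everyone at 5 mg bid. Section 8.6.1 makes increases optional, "starting at the Week 4 visit and at subsequent study visits. Dose increases can occur no more frequently than every 4 weeks", subject to platelet and neutrophil criteria. Protocol Section 7.1 gives the extended phase as "132 weeks; subjects receiving benefit will continue ruxolitinib treatment until Week 156".

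**Person-time.** SAP Section 6.4 plans total patient-years. The Table 14.3.1.1 shell splits them by final titrated dose group through Week 24, in bands that differ from the adverse event bands.

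**The concern.** A subject who passes through a dose in 4 weeks and one who stays on it for months each add one to that column's denominator, but the second has far longer to have an event there. The columns then differ through time at risk even if the drug is equally toxic at every dose.

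Readers will compare the columns. SAP Section 5.9.3.3 counts adverse events by dose among its dose-response type analyses, and the protocol has the secondary objective "To determine an appropriate dosing strategy for patients with low platelets". A pattern produced by exposure time could be read as toxicity rising with dose, or a real rise could be hidden.

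Nothing else planned gives event rates by dose. The life-table hazards in SAP Section 8.1 cover Grade 4 thrombocytopenia, Grade 2 or higher hemorrhage and Grade 4 anemia, and are not stated to be by dose. The longitudinal analysis in SAP Section 9.5 addresses platelets only.

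**Working it through.** **1. The denominator in the shell.** The any-event row of Table 14.3.2.2.2 (illustrative draft output, not results) reproduces as n/N: 3/23 = 13.0%, 5/14 = 35.7%, 1/7 = 14.3%. The column Ns are 2 + 23 + 14 + 7 + 1 = 47 for 23 subjects, so subjects are counted in every column they entered.

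**2. Inputs.** Start at 10 mg/day, first increase at Week 4, steps of 5 mg/day at least 4 weeks apart, core phase 24 weeks (Protocol Sections 7.1, 8.1 and 8.6.1). Assumptions not in the documents: a constant hazard h, equal at every dose, of 0.5 per year (0.25 as a check), and the escalation paths and mixes below.

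**3. Formula.** The expected percentage with at least one event during w weeks at a dose is 1 − exp(−h × w × 7/365.25). At h = 0.5:
- 4 weeks: 1 − exp(−0.0383) = 3.8%
- 8 weeks: 1 − exp(−0.0767) = 7.4%
- 12 weeks: 1 − exp(−0.1150) = 10.9%
- 16 weeks: 1 − exp(−0.1533) = 14.2%
- 24 weeks: 1 − exp(−0.2300) = 20.5%

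**4. Columns with no true dose effect, h = 0.5 per year**

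| Escalation | 10 mg/day | 15 mg/day | 20 mg/day |
|---|---|---|---|
| Fastest core path, 4/4/16 weeks | 3.8% | 3.8% | 14.2% |
| 8/4/12 weeks | 7.4% | 3.8% | 10.9% |
| 25% stay at 10 mg/day for 24 weeks, 75% follow 8/4/12 | 10.7% | 3.8% | 10.9% |
| Late mix | 14.7% | 7.3% | 7.4% |

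- Third row, first entry: 0.25 × 20.5 + 0.75 × 7.4 = 10.7.
- Late mix: 40% stay at 10 mg/day for 24 weeks; 30% have 12 weeks at 10 and 12 at 15; 30% have 12 weeks at 10, 4 at 15 and 8 at 20. The entries are 0.4 × 20.5 + 0.6 × 10.9 = 14.7; (10.9 + 3.8)/2 = 7.3; and 7.4.

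At h = 0.25 the fastest path gives 1.9%, 1.9% and 7.4%.

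**5. Effect of the lowest-dose rule.** If a repeated event of equal grade is counted only at the lowest dose, the higher columns lose subjects who already had it, but those subjects stay in the denominators. In the late mix the 15 mg/day entry becomes exp(−0.1150) × 7.3 = 6.5%, and the 20 mg/day entry becomes exp(−0.1533) × 7.4 = 6.3%. This is a second distortion, separate from time.

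**6. What a rate would show.** First events divided by patient-years at risk at that dose has expectation h, here 50 per 100 patient-years, in every column of every row above.

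**The case against.** **No fixed direction.** With a flat hazard the columns can rise, stay nearly level or fall. The nearly fourfold gradient belongs to one fastest titrator. Protocol Section 4.1.5 reports that most interim subjects reached 10 mg bid at about Week 13, which is closer to the 8/4/12 path, where 20 versus 10 mg/day differs about 1.5-fold. This stands. A reader might infer that the tables will show toxicity rising with dose; the documents support only that they can mislead.

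**The extension.** It is tempting to carry 20 mg/day through to Week 156 and quote a far larger gradient. Protocol Section 8.6.1 allows increases to 25 mg bid in that phase, so a fixed dose is not a documented scenario. The SAP is also written to Amendment 1, with a 24-week treatment phase. Longer treatment can widen the imbalance, but no figure for it is relied on here.

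**Link to the dosing objective.** A reader might infer that these tables are the main evidence for it. No section says so, and the platelet analysis in SAP Section 9.5 also bears on dose. The link is reasonable but inferred.

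**Rates have their own bias.** Only subjects with adequate platelets and neutrophils escalate, so time at higher doses comes from selected tolerators, and risk may not be constant within a dose. This stands: rates should sit beside the percentages and not replace them.

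**Grouping is unsettled.** SAP Section 5.2 groups these summaries by final titrated daily dose, whereas the shells use dose ever received. That conflict has to be settled in the same edit.

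None of this makes the crude percentages comparable across columns.

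**Conclusion.** The point holds as a limitation of descriptive safety tables. Crude percentages of subjects ever at a dose, with unequal time at each dose, can create or mask a dose-toxicity pattern, and no person-time at each dose or exposure-adjusted adverse event rate by dose is planned. In the illustrations, 20 mg/day relative to 10 mg/day runs from nearly fourfold higher to about half (7.4% against 14.7%) with no dose effect at all. Those sizes rest on the assumed hazard and paths; the unequal time rests on the protocol's titration rules. The co-primary correlation tests are unaffected. Adding rates is worthwhile and cheap, but it does not turn the tables into unbiased dose-response evidence.

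**What to change.** In the by-dose tables listed above:

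1. From the EX domain, add patient-years at each dose class and first events per 100 patient-years, with 95% confidence intervals, beside the existing n and %. Count time only until the subject's first event of that type. Allocate interruption days in line with the last non-zero dose rule.
2. For these rates, assign each first event to the dose at its onset under SAP Section 5.9.3.4 rather than by the lowest-dose rule.
3. Show the core phase separately from the whole study.
4. Reconcile SAP Section 5.2 (final titrated dose) with the shells (dose ever received).
5. State in a footnote that the rates assume roughly constant risk within a dose, do not remove selection into higher doses, and are descriptive, to be read with the crude percentages.

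The cost is SAP wording and programming. The SAP already uses EX dosing data for its dose-response analyses, so no new data or protocol change is needed.
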